## 5. GENERAL METHODOLOGY AND CONVENTIONS

All analyses will be performed after completion of the study.

### 5.1. Hypotheses and Decision Rules

The primary immunogenicity objective of the study is to assess the immunogenicity of the investigational product by NT in Japanese healthy adults (16 years of age and older) and children ( $\geq 1$  to  $<16$  years of age) when administered on a 3-dose schedule. The null hypothesis to be tested concerns the seropositivity rate for the primary endpoint in each age group. The immune response induced by TBE vaccine will be evaluated in each age group, testing the hypotheses  $H_0$ : seropositivity rate  $\leq 90\%$  vs  $H_1$ : seropositivity rate  $> 90\%$ . These hypotheses will be tested by age group separately and no adjustment of multiplicity will be considered. For each age group, if the lower bound of the 95% CI on the NT seropositivity rate among the evaluable population is  $> 90\%$ , the objective is achieved.

### 5.2. General Methods

Descriptive summary statistics will be provided for all endpoints. Unless otherwise explicitly stated, descriptive statistics for continuous variables are n, mean, median, standard deviation, minimum, and maximum. Descriptive statistics for categorical variables are the proportion (%) and the n (the numerator) and N (the denominator) used in the calculation of the proportion.

All of the safety, tolerability, and immunogenicity data will be summarized by age group.

### **5.2.1. Analyses for Binary Endpoints**

The number and percentage of participants in each category will be summarized. The 95% CI for percentage will also be presented, where appropriate.

The 95% CI for the proportion will be constructed by the Clopper-Pearson method described by Newcombe. The 95% CI will be presented in terms of percentage. For the endpoint to be tested, evaluating 95% CI based on the Clopper-Pearson method comparing its lower limit to 90% corresponds to the statistical testing with the exact method.

### **5.2.2. Analyses for Continuous Endpoints**

Unless otherwise specified, the CI for the mean of the continuous variables will be constructed by the standard method based on Student's t distribution.

#### **5.2.2.1. Geometric Mean (GM)**

Continuous immunogenicity endpoints will be logarithmically transformed for analysis. GMT CCI and associated 2-sided 95% CI will be calculated at each available time point. The GM and associated 2-sided 95% CI will be calculated as the mean of the assay results on the natural logarithmic scale based on Student's t distribution and then exponentiating the results.

#### **5.2.2.2. Geometric Mean Fold Rise (GMFR)**

GMFR will be calculated as the mean difference of an individual participant's logarithmically transformed antibody levels (postvaccination minus prevaccination) and back transformed to the original scale. Two-sided 95% CIs will be obtained by constructing CIs using 1-sample Student's t distribution for the mean difference of measures on the logarithmically transformed assay results and transforming the limits back to the original scale.

#### **5.2.2.3. Reverse Cumulative Distribution Curves (RCDCs)**

Empirical RCDCs for TBEV-neutralizing antibody titers will be generated by each combination of available time points and age groups.

### **5.3. Methods to Manage Missing Data**

#### **5.3.1. Immunogenicity Data**

Titers below the LLOQ or denoted as BLQ will be set to  $0.5 \times \text{LLOQ}$  for analysis.

Values that are designated as serum quantity not sufficient (QNS), designated as indeterminate results (IND), or recorded as "not done" will be set to missing. No imputation will be done for these missing values.

### **5.3.2. Safety Data**

Standard algorithms on handling missing AE dates and missing AE severity will be applied as described in Pfizer's Vaccine Statistics Rulebook.

### **5.3.3. Reactogenicity Data**

For derived variables based on reactogenicity data, if any day of the 7-day e-diary is available, the “any day (Day 1-7)” data will be considered nonmissing.

The reactogenicity data are collected through the e-diary, which does not allow participants to skip the question. Therefore, for a specific day, as long as the e-diary data are transmitted for that day, all of the reactogenicity data for the participant on that day are nonmissing. No missing reactogenicity data will be imputed other than what is described in [Section 3.5.2](#).

## **6. ANALYSES AND SUMMARIES**

### **6.1. Primary Endpoints**

#### **6.1.1. Seropositivity Based on TBE-Neutralizing Antibody Levels (Achieving NT Titer $\geq 1:10$ ) 4 Weeks After the Third Dose**

##### **6.1.1.1. Main Analysis**

- Estimand strategy: Hypothetical ([Section 2.1](#)).
- Analysis set: Evaluable immunogenicity population ([Section 4](#)).
- Analysis methodology: Exact testing of the binomial proportion and descriptive summary statistics.
- Intercurrent events and missing data: For participants who discontinue, all collected data will be included; intermediate missing values will not be imputed.
- Reporting summaries: n (the number of seropositive participants), N (the size of the analysis population), point estimate (seropositivity rate), and the exact 2-sided 95% CI will be calculated using the Clopper-Pearson method for the seropositivity rate based on the immune response determined by NT 4 weeks after the third vaccination. NT titers  $\geq 1:10$  are considered seropositive.

CCI

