7. DISCONTINUATION OF STUDY INTERVENTION AND PARTICIPANT DISCONTINUATION/WITHDRAWAL

7.1. Discontinuation of Study Intervention

In rare instances, it may be necessary for a participant to permanently discontinue study intervention (definitive discontinuation). Reasons for definitive discontinuation of study intervention include the following: a participant no longer meets the eligibility criteria during the vaccination period of the study (eg, pregnancy).

Note that discontinuation of study intervention does not represent withdrawal from the study. Per the study estimands, if study intervention is definitively discontinued, the participant will remain in the study to be evaluated for safety. See the SRM for data to be collected at the time of discontinuation of study intervention and follow-up for any further evaluations that need to be completed.

In the event of discontinuation of study intervention, it must be documented on the appropriate CRF/in the medical records whether the participant is discontinuing further receipt of study intervention or also from study procedures, postvaccination study follow-up, and/or future collection of additional information.

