7.2. Participant Discontinuation/Withdrawal From the Study

A participant (or legally acceptable representative/parent/legal guardian if the participant is 1 to <20 years of age) may withdraw from the study at any time at his/her own request. Reasons for discontinuation from the study may include the following:

- Refused further follow-up;
- Lost to follow-up;
- Death;
- Study terminated by sponsor;
- AEs/SAEs;
- Protocol deviation;
- Physician decision;
- Request by the participant or participant's legally acceptable representative/parent/legal guardian;
- No longer meets eligibility criteria;
- Pregnancy.

If a participant does not return for a scheduled visit, every effort should be made to contact the participant or participant's parent(s)/legal guardian(s). All attempts to contact the participant or participant's parent(s)/legal guardian(s) and information received during contact attempts must be documented in the participant's source document. In any circumstance, every effort should be made to document participant outcome, if possible.

At the time of discontinuation, please refer to the ISF and SRM for assessments to be collected at the time of study discontinuation and follow up and for any further evaluations that need to be completed.

The participant should be requested to return for a final visit, if applicable, and the investigator will perform the procedures indicated for the next visit. Any AEs or SAEs that are continuing at the time of withdrawal from the study should be followed until resolution or, in case of permanent impairment, until the condition stabilizes.

If a participant withdraws from the study, he/she or the participant's parent(s)/legal guardian(s) may request destruction of any remaining samples taken and not tested, and the investigator must document any such requests in the site study records and notify the sponsor accordingly.

If the participant withdraws from the study and also withdraws consent (see Section 7.2.1) for disclosure of future information, no further evaluations should be performed and no additional data should be collected. The sponsor may retain and continue to use any data collected before such withdrawal of consent.

Lack of completion of all or any of the withdrawal/early termination procedures will not be viewed as protocol deviations so long as the participant's safety was preserved.

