9.1.1. Estimands

9.1.1.1. Immunogenicity

9.1.1.1.1. Primary Estimand

The primary estimand is seropositivity rate based on TBEV-neutralizing antibody levels (achieving NT titer $\geq 1:10$) 4 weeks after the third dose for the evaluable population (Section 9.3).

This estimand estimates the immunogenicity in the hypothetical setting where participants follow the study schedules and protocol requirements as directed. Missing serology results are not imputed, as MCAR is assumed. For participants who discontinue the study or have major protocol violations, all postdiscontinuation or postviolation observations will be censored.

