9.1.1.1.2. Secondary Estimands

The secondary estimands of this study are following for the evaluable population.

- Seropositivity rate based on TBEV-neutralizing antibody levels (achieving NT titer $\geq 1:10$) 4 weeks after the second dose.
- NT GMTs 4 weeks after the second and 4 weeks after the third dose.
- NT GMFRs 4 weeks after the second and 4 weeks after the third dose as compared to baseline.
- NT GMFR 4 weeks after the third dose as compared to 4 weeks after the second dose.

These estimands estimate the immunogenicity in the hypothetical setting where participants follow the study schedules and protocol requirements as directed. Missing serology results are not imputed, as MCAR is assumed. For participants who discontinue the study or have major protocol violations, all postdiscontinuation or postviolation observations will be censored.

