## 2.1. Study Objectives, Endpoints, and Estimands

The estimands corresponding to each primary, secondary, CCI [REDACTED] objective are described in Table 2 below.

The primary estimand of this study is the hypothetical estimand, which estimates the vaccine immune response in the hypothetical setting where participants follow the study schedule and protocol requirements as directed. It includes the following 4 attributes:

- Population: Healthy Japanese adult participants 16 years of age and older who received 3-dose TBE vaccine 0.5 mL in compliance with the key protocol criteria (evaluable adult participants [Section 4]) and healthy Japanese pediatric participants  $\geq 1$  to  $<16$  years of age who received 3-dose TBE vaccine 0.25 mL in compliance with the key protocol criteria (evaluable pediatric participants [Section 4]);
- Variable: Seropositivity based on TBEV-neutralizing antibody levels (achieving NT titer  $\geq 1:10$ ) 4 weeks after the third dose;
- Intercurrent event: All data after an intercurrent event (protocol deviation, discontinuation of the study, etc.), if collected, will be excluded. Major protocol violations will be determined by clinical review (through the data handling memo);
- Population-level summary: The proportion of participants who are seropositive 4 weeks after the third dose in each age group.

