## 4. ANALYSIS SETS (POPULATIONS FOR ANALYSIS)

Data for all participants will be assessed to determine if participants meet the criteria for inclusion in each analysis population prior to releasing the database and classifications will be documented per standard operating procedures. For purpose of analysis, the following populations are defined for each age group.

Population	Description
Enrolled	"Enrolled" means that a participant, or his or her legally authorized representative, has agreed to participate in a clinical study following completion of the informed consent process and is deemed eligible to participate. Potential participants who are screened for the purpose of determining eligibility for the study, but do not participate in the study, are not considered enrolled, unless otherwise specified by the protocol.
Evaluable immunogenicity	All participants who are eligible, receive all 3 doses of the investigational product, have blood drawn for assay testing within the specified time frame for baseline and 4 weeks (21-35 days) after the third vaccination, have valid and determinate assay result (NT titer) at baseline and 4 weeks after the third vaccination visit, are NT seronegative (NT titer <1:10) at baseline, and have no major protocol violations.
Evaluable immunogenicity for the second dose	All participants who are eligible, receive the first 2 doses of the investigational product, have blood drawn for assay testing within the specified time frame for baseline and 4 weeks (21-35 days) after the second vaccination, have valid and determinate assay result (NT titer) at baseline and 4 weeks after the second vaccination visit, are NT seronegative (NT titer <1:10) at baseline, and have no major protocol violations.

Population	Description
All-available immunogenicity	All enrolled participants who receive at least the first 2 doses of the investigational product and have valid and determinate assay results (NT titer CCI ) 4 weeks after the second and/or the third vaccination.
Safety	All enrolled participants who receive at least 1 dose of the investigational product.

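### Do the SAP's wording on participants who discontinue and its choice of population for dose-2 seropositivity put any result at risk?

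*SAP*

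**What the plan says.** **Discontinuation.** SAP 6.1.1.1 (primary), 6.2.1.1 (dose-2 seropositivity) and 6.2.2.1 (NT titers) carry the same line: "For participants who discontinue, all collected data will be included; intermediate missing values will not be imputed". SAP 2.1, describing the primary estimand, says: "All data after an intercurrent event (protocol deviation, discontinuation of the study, etc.), if collected, will be excluded". Protocol 9.1.1.1.1 says "all postdiscontinuation or postviolation observations will be censored", and protocol 9.1.1.1.2 repeats the rule for the secondary estimands: "For participants who discontinue the study or have major protocol violations, all postdiscontinuation or postviolation observations will be censored". All three SAP analyses name the hypothetical strategy, and 6.1.1.1 refers to Section 2.1 for it.

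Protocol 7.1 separates stopping vaccination from leaving the study ("discontinuation of study intervention does not represent withdrawal from the study"). Protocol 7.2 asks a withdrawing participant to return for a final visit, where "the investigator will perform the procedures indicated for the next visit".

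**Population.** Protocol 9.1.1.1.2 opens: "The secondary estimands of this study are following for the evaluable population". The protocol's evaluable set requires all three doses, and SAP Table 2 also places dose-2 seropositivity in three-dose participants. SAP 4 defines a further set, evaluable for the second dose. It requires two doses, in-window samples at baseline and 4 weeks after dose 2, and valid NT results at both. SAP 6.2.1.1 uses only this set. SAP 6.2.2.1 uses the three-dose set and adds the second-dose set for dose-2 titers. The exclusion summary in SAP 6.5.2 does not name the second-dose set.

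**The concern.** Read literally, the sentence in the analysis sections keeps data that the estimand sections discard. It sets no limit at the time of discontinuation and does not say whether leaving the study or stopping vaccination is meant. If two analysts could build different datasets for the primary test, its result could depend on which section they followed.

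Dose 2 looks more exposed. A participant who withdraws between dose 2 and Visit 3 and attends the final visit 21 to 35 days after dose 2 could satisfy the second-dose definition. The documents do not say whether that sample counts as taken after discontinuation.

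The population mismatch raises a second worry. A reported secondary rate and its interval would rest on a different group from the one SAP Table 2 names, with no stated table of reasons for exclusion from its denominator.

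**Working it through.** **1. The plan's own figures.** Inputs from protocol 9.2: 90 adults at 99.4%, 60 children at 99.6%, success if the Clopper-Pearson lower 95% limit exceeds 90%.

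- Adults: 87/90 gives a lower limit of 90.57% and 86/90 gives 89.01%, so at most 3 seronegatives are allowed. Power = P(X ≥ 87) = 99.78% (stated: above 99%).
- Children: 59/60 gives 91.06% and 58/60 gives 88.47%, so at most 1 is allowed. Power = P(X ≥ 59) = 97.57% (stated: 97.3%).

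The figures agree closely, and neither depends on the mismatches.

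**2. Can the discontinuation sentence reach the primary test?** The evaluable participant must have received three doses and "have blood drawn for assay testing within the specified time frame for baseline and 4 weeks (21-35 days) after the third vaccination". That sample is taken at Visit 5, the last visit, so anyone who left the study earlier without it is already outside the set under either rule.

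Suppose nevertheless that exactly one evaluable participant counts as a discontinuer. Removing that person leaves 89 adults (86/89 has lower limit 90.46%, so 3 seronegatives are still allowed) or 59 children (58/59 has 90.91%, so 1 is still allowed). The conclusions differ only if this participant is seronegative and the others hold exactly the allowed number of seronegatives. With q the seronegative probability:

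- Children: 0.004 × Binomial(1; 59, 0.004) = 0.004 × 0.1870 = 0.00075, or 0.075%.
- Adults: 0.006 × Binomial(3; 89, 0.006) = 0.006 × 0.0146 = 0.00009, or 0.009%.

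**3. One final-visit sample at dose 2.** The documents give no expected dose-2 rate, so p = 80% to 98% is assumed. Adding one seronegative sample to n others lowers the rate by p/(n+1); adding one seropositive raises it by (1−p)/(n+1).

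| | n | one seronegative | one seropositive |
|---|---|---|---|
| Adults | 90 | −0.88 to −1.08 points | +0.22 to +0.02 |
| Children | 60 | −1.31 to −1.61 points | +0.33 to +0.03 |

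Under protocol 7.2 the final visit follows the next scheduled visit. After dose 2 that is Visit 3, so an in-window sample is in substance the planned Visit 3 draw.

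**4. Second-dose set against three-dose set.** Neither set contains the other: one does not require dose 3, and the other does not require a Visit 3 result. As an illustration with assumed counts, let A be in both sets and C only in the second-dose set. Comparing the second-dose set (A + C) with A, the difference in rates is C/(A+C) × (rate in C − rate in A).

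| | A, C | C equal to A | C 10 points lower | C 20 lower | C 5 higher |
|---|---|---|---|---|---|
| Adults | 87, 10 | 0 | −1.03 | −2.06 | +0.52 |
| Children | 58, 5 | 0 | −0.79 | −1.59 | +0.40 |

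A visible shift needs participants who miss the third-dose criteria to respond quite differently to the first two doses.

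**5. Denominator.** In SAP 6.2.1.1, N is the size of the second-dose set. Every member of that set has a valid dose-2 result, so N is correct there and no missing result is counted as a non-response.

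**The case for a change.** The strongest case for a change is that both conflicts sit inside the current SAP and would be cheap to correct. SAP 6.1.1.1 points to Section 2.1 and, in the same list, gives a line that literally contradicts it. The freedom to modify the protocol (protocol 9, SAP 2) permits a different dose-2 population, but it does not reconcile SAP Table 2 with SAP 6.2.1.1. SAP 6.2.2.1 reports dose-2 titers in both sets, and 6.2.1.1 visibly does not do the same for seropositivity.

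That stands as a description of the text, but it does not carry through to the results:

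- **Discontinuers.** The hypothetical strategy named in all three analyses, together with the protocol's censoring rule for primary and secondary estimands, leads to one reading: data up to study discontinuation are used and later data are not.
- **Population.** The second-dose set has its own definition in SAP 4 and is used in 6.2.1.1, 6.2.2.1 and 6.4. It is deliberate. For a result 4 weeks after dose 2, it avoids conditioning on what happens months later at dose 3.
- **Three-dose result.** SAP 6.2.2.1 also gives, in the three-dose set, proportions with titer at or above the LLOQ at each time point with exact intervals. If the LLOQ is 1:10, which the visible text does not state, that is dose-2 seropositivity on the SAP Table 2 population. Redacted text after 6.2.1.1 may hold a further analysis. An extra table could therefore duplicate one already planned.
- **Exclusions.** SAP 6.5.2 tabulates, for each vaccination, who was vaccinated and who had blood drawn inside or outside the window, and it lists protocol deviations. Only the summary of reasons for exclusion from the second-dose set is not named.

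**Conclusion.** No change follows. Carried out as written, the plan gives sound results. The discontinuation sentence is practically inert for the primary test: the chance of opposite conclusions is 0.075% in children and 0.009% in adults, given one evaluable discontinuer and the planned response rates. The primary conclusion and its power are unaffected.

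Dose-2 seropositivity is descriptive and untested. One disputed sample moves it by at most about 1.1 points in adults and 1.6 in children. The choice between the two sets moves it by up to about 2 points if those only in the second-dose set respond 20 points worse. These dose-2 figures rest on assumed rates of 80% to 98% and on illustrative set sizes, because the documents give neither; they are not forecasts. What is left is an entry in SAP Table 2 and a loosely worded line, both of which the analyst can resolve from the rest of the SAP and protocol.

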## 6.1.2. Safety Endpoints

### 6.1.2.1. Adverse Events

It should be recognized that most studies are not designed to reliably demonstrate a causal relationship between the use of a pharmaceutical product and an AE or a group of AEs. Except for select events in unique situations, studies do not employ formal adjudication procedures for the purpose of event classification. CCI

- Endpoints: Participants reporting AEs and SAEs categorized according to MedDRA ([Section 3.5.1](#)).
- Analysis time points: From the time of informed consent through and including Visit 5 (1 month after the third vaccination):
  - After the first vaccination (Visit 1) and before the second vaccination (Visit 2)
  - After the second vaccination (Visit 2) and before the 1-month blood draw after the second vaccination (Visit 3)
  - After the third vaccination (Visit 4) and before the 1-month blood draw after the third vaccination (Visit 5)
  - During the vaccination phase
- Analysis population: Safety population ([Section 4](#)). Participants who lack any safety data will be excluded from that analysis.
- Reporting summaries:  
For each of the following AE categories, the number and percentage of participants reporting at least 1 event of each preferred term, arranged by system organ class with the associated Clopper-Pearson 95% CI. For deaths, only a listing will be provided.
  - AEs reported within 1 month after each vaccination
  - Related AEs reported within 1 month after each vaccination
  - SAEs reported throughout the study
  - Related SAEs reported throughout the study
  - Severe or life-threatening AEs reported within 1 month after each vaccination
  - Related severe or life-threatening AEs reported within 1 month after each vaccination
  - AEs leading to discontinuation reported within 1 month after each vaccination

- Related AEs leading to discontinuation reported within 1 month after each vaccination
- Immediate AEs reported within 1 month after each vaccination

Listings of participants reporting any AE and immediate AEs and listings of all reported AEs will be generated. In addition, AEs occurring after participants signed the informed consent and prior to vaccination will also be listed.

